4.1.3 Serious Adverse Events (SAEs)

A Serious Adverse Event (SAE) is an AE, as defined for this trial (see 4.1.1), that fulfils one or more of the following criteria:

- Results in death.
- Is immediately life-threatening.
- Requires hospitalisation or prolongation of existing hospitalisation.
- Results in persistent or significant disability or incapacity.
- Is a congenital abnormality or birth defect.
- Immediate intervention was required to prevent one of the above or is an important medical condition.

For the purposes of this trial, as with AEs, we will only collect SAEs related to the participant's treated knee, to the treatment they receive in the trial (or any treatment for their knee) or related to trial processes.

Further knee surgery only needs to be reported as an SAE if it results from a complication of the allocated trial treatment (such as infection). Persistent pain without new pathology or other event will not be considered an SAE as this will be recorded in outcome scores.

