4.1.2 Recording adverse events

AEs related to the surgical procedure including the surgery, anaesthetic, post-operative care and rehabilitation, any component of the Personalised Knee Therapy package, or any knee treatment in the AE reporting period will be recorded on the appropriate CRF for return to the trial central office and reported to the relevant oversight committees.

AEs related to the treated knee, treatment received in the trial (or any treatment for their treated knee) or related to trial processes will be collected from the point of randomisation onwards, up to 24-months.

Some events which occur during treatment and recovery will be considered normal aspects of the therapy, anaesthetic and post-operative recovery process and will not need reporting as AEs or SAEs unless in the opinion of the clinical team, they are untoward, excessive, or outside of what might normally be expected for the procedure. These are normal events that occur frequently after physiotherapy or surgery and include:

- Nausea and/or vomiting after surgery.
- Drowsiness or headache after surgery.
- Temporary low blood pressure after surgery.
- Sore throat after surgery.
- Itching after surgery.

- Post-operative or post-intervention pain in the first six months (note that pain after six months will be collected as an outcome in the study, using the KOOS pain domain).
- Numbness on the lateral side of the surgical wound.
- Early wound oozing which spontaneously resolves.
- Swelling, within the confines of what is considered normal post-intervention swelling by the treating clinical team.
- Restriction of range of motion, within the confines of what is considered normal post-operatively by the treating clinical team.
- Bruising, unless this is considered abnormal by the treating clinical team.
- Post-intervention pain, muscle soreness or tiredness during or after physiotherapy
 (in-patient and out-patient) in either group.
- Ongoing instability symptoms.

All recorded AEs will be monitored for trends, see section 4.2 for responsibilities. An outcome of 'not yet resolved' is an acceptable final outcome for non-serious AEs at the end of a patient's participation in a trial.

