4.1.7 Assessment of Expectedness

Where reported, SAEs will be assessed for having a possible causal relationship with the intervention or its associated procedures. Where a causal relationship is established an evaluation of expectedness will be made by the CI or their delegate, using the list below. The following are SAEs that are expected as a result of the intervention and its associated procedures:

Those related in general to surgery and anaesthetic:

- Injury to teeth, mouth, or throat during anaesthetic.
- Chest infection.
- Nerve or vessel injury due to local anaesthetic (i.e., local blocks or spinal anaesthetic).
- Spinal haematoma.
- Stroke or Cardiac Event.
- Death.

Those related to the operation itself or physiotherapy:

- Exacerbation/persistence of knee pain or instability beyond what is considered
 normal by the treating clinical team. As this outcome will be captured in Patient
 Reported Outcome Measures (PROMs) throughout the study, only medical or
 surgical interventions for persistent knee pain need to be reported.
- Restriction of range of motion, including need for manipulation under anaesthetic,
 arthroscopic or open procedures to relieve stiffness.
- Infection.
- Wound healing problems.
- Fracture, ligament or tendon damage or rupture.

- Revision surgery or other corrective surgery.
- Irritation from metalwork or surgery to remove metalwork.
- Thrombosis (deep vein thrombosis, pulmonary embolus, cerebral infarct).
- Damage to nerves or vessels.
- Persistent muscle soreness or muscle injury.
- Bruising.
- Swelling.
- Skin damage (for example, from bracing).
- Exercise-related fatigue.

Treatments of expected events listed above (such as surgery for infection or wound problems) are also expected events.

If the SAE is not listed above and is considered to have at least a possible causal relationship to the intervention, the event would therefore be classified as unexpected and will be reported to the REC within 15 days.

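### Protocol sections 4.1.3 and 4.1.7 give different answers on whether an operation for persistent knee pain, without a complication, is reported as an SAE

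*Protocol*

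**What the plan says.** Section 4.1.3 has two adjacent sentences on this. On surgery: "Further knee surgery only needs to be reported as an SAE if it results from a complication of the allocated trial treatment (such as infection"). On pain: "Persistent pain without new pathology or other event will not be considered an SAE as this will be recorded in outcome scores".

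Section 4.1.7 introduces its list with "The following are SAEs that are expected as a result of the intervention and its associated procedures". The first bullet under the operation or physiotherapy covers exacerbation or persistence of knee pain or instability beyond what the clinical team considers normal. It notes that patient-reported outcomes capture this, and concludes that only medical or "surgical interventions for persistent knee pain need to be reported". Later bullets include "Revision surgery or other corrective surgery" and "Irritation from metalwork or surgery to remove metalwork".

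Three other places bear on the point:
- Section 4.1.2 lists "Ongoing instability symptoms" among the normal events that are not reported unless judged untoward or excessive.
- Section 4.1.4 sends sites to 4.1.2 and 4.1.3 for the SAE reporting criteria and does not mention 4.1.7.
- Section 3.1.1.2 lists adverse events and further knee surgery (either arm) as separate secondary outcomes at six, 12, 18 and 24 months.

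**The concern.** The 4.1.7 sentence tells the reader what to report, although it sits in a list whose purpose is to classify events already reported. It drops the condition that 4.1.3 puts on further surgery. Two sites with the same event, an operation for persistent knee pain with no complication behind it, could each point to a protocol sentence and do opposite things.

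Adverse events are a secondary outcome, and under section 4.2 the DMC reviews safety by allocation group. SAEs are due within 24 hours of awareness (4.1.4), so sites must decide quickly from this text; section 7.2.1 counts 27 sites. The protocol expects some PKT participants to have surgery later (1.2.1, 6.1), so the event is foreseeable. If sites differ in practice, SAE counts stop being comparable between sites, and possibly between arms.

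**Working it through.** **Passages side by side**

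- Persistent pain itself: 4.1.3 excludes it, and 4.1.7 leaves it to the patient-reported outcomes. No conflict.
- Operation for persistent pain caused by a complication of the allocated treatment: reportable under both. No conflict.
- Operation for persistent pain without such a complication: excluded by 4.1.3 ("Further knee surgery only needs to be reported as an SAE if it results from a complication of the allocated trial treatment"), to be reported under 4.1.7. **Conflict.**
- Operation for instability without a complication: excluded by 4.1.3. The 4.1.7 bullet names instability, but its reporting sentence names only knee pain. Unclear rather than contradictory.
- Corrective surgery and metalwork removal: listed in 4.1.7 as expected SAEs without the complication condition, but with no instruction to report. They add doubt, not a second contradiction.

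**Can the effect be sized?**

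The protocol states no expected SAE rate, so there is no SAE figure to reproduce. The number per arm does reproduce: 110 / (1 − 0.20) = 137.5, rounded up to 138, and 2 × 138 = 276.

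Inputs for an illustration:
- Complications of MPFL reconstruction 3–7% (1.2.2): 138 × 0.03 = 4.1 and 138 × 0.07 = 9.7, so about 4 to 10 surgery-arm events.
- Crossover *c*: Table 4 sets red at 20%. This is a stop-go threshold, not a forecast. 138 × 0.20 = 27.6; at an assumed 10%, 13.8.
- Share *f* of delayed operations done for pain: not in the protocol, so left free from 0 to 1.

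Extra PKT events if 4.1.7 is followed = 138 × *c* × *f*. If 4.1.3 is followed, they are 0.

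The arms tie when *f* = complication rate / *c*:
- *c* = 20%: 0.03 / 0.20 = 15% to 0.07 / 0.20 = 35%.
- *c* = 10%: 0.03 / 0.10 = 30% to 0.07 / 0.10 = 70%.

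Fisher exact p-values, PKT v surgery, 138 per arm (illustrative; the protocol names no test of SAE counts):
- 0 v 4: 0.12; 0 v 10: 0.0016.
- 7 v 4: 0.54; 7 v 10: 0.62 (7 is *c* = 20%, *f* = 25%).
- 28 v 10: 0.0026 (28 is *c* = 20%, *f* = 100%).

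The same broad use of 4.1.7 would add events in the surgery arm. Screw removal follows 30–50% of tibial tubercle osteotomies (1.2.2), and 30–50% of patients have patella alta (2.8.1.2). If all of those had the osteotomy, 138 × 0.3 × 0.3 = 12.4 to 138 × 0.5 × 0.5 = 34.5 events are added. The surgery arm then has 138 × (0.03 + 0.09) = 16.6 to 138 × (0.07 + 0.25) = 44.2. Against at most 27.6 in the PKT arm, a PKT excess at the lower end needs *f* above 0.12 / 0.20 = 60%. At the upper end, or at 10% crossover (13.8), it cannot occur. Re-operations for pain in the surgery arm would add more, at a rate the protocol does not give.

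The sign therefore depends on *c*, on *f* and on how broadly 4.1.7 is read, and the protocol fixes none of them.

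**The case against.** The strongest reply is that precedence is already settled. Section 4.1.4 names 4.1.2 and 4.1.3 as the reporting criteria. Section 4.1.7 applies to SAEs already reported, once a causal link is established, and is carried out by the chief investigator or a delegate, not by the site deciding whether to submit a form. Section 4.2 adds central verification of SAEs and monthly review, and delayed operations are not lost because further knee surgery is its own outcome. Most of this stands, and it makes 4.1.3 the more natural rule. It does not remove the 4.1.7 sentence, which is phrased as an instruction to report: if 4.1.3 governs, that sentence is wrong where it stands. The further-surgery outcome records the operation but does not make SAE counts consistent between sites.

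A reader might infer something stronger: that all delayed operations in the PKT arm are affected, and that the SAE comparison could reverse. The documents do not support this. The reporting sentence covers interventions for knee pain only. Surgery for instability is not named there, and the population has recurrent dislocation. The ambiguity also reaches re-operations in the surgery arm. A reversal needs a threshold read as a forecast, a pain share with no source, and 4.1.7 applied broadly to one arm only.

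**Conclusion.** The point holds in a narrow form. For one kind of event, an intervention for persistent knee pain without a complication of the allocated treatment, 4.1.3 and 4.1.7 give different answers, in either arm. The conflict lies between the further-surgery sentence of 4.1.3 and the 4.1.7 bullet; on pain itself the sections agree.

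The effect on the between-arm SAE comparison is unknown in size and direction. The counts above are illustrations. They assume 138 per arm, every surgery-arm participant operated on, one event per person, and every complication meeting a seriousness criterion. The consequence is limited to a secondary safety outcome and the DMC's safety tables. It is worth correcting because the correction is cheap and the event foreseeable.

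**What to change.** Reconcile 4.1.3 and 4.1.7 into a single SAE reporting rule for interventions for persistent knee pain, say whether it also covers instability, and apply it identically in both arms. Confine 4.1.7 to classifying expectedness by removing its reporting instruction, or by moving it to 4.1.3 if the sponsor means it to apply. The reconciliation should not alter in passing the reference in 4.1.3 to the allocated treatment; widening that to any treatment received would be a separate, substantive decision.

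Then notify sites, and check SAE forms already received against the reconciled rule before the DMC and final safety tables are produced. The cost is a wording amendment, a note to sites and one check of existing forms.

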4.1.4 Reporting SAEs and Related SAEs

The SAE form should be completed in the electronic database in the first instance. This can then be followed up by an email to the study resource account [contact] and the [contact] resource account.

All **SAEs** that meet the reporting criteria for this trial (see section 4.1.2 and 4.1.3) occurring from the time of randomisation until 24-months post-randomisation, must be detailed on the SAE Form and reported **within 24 hours** of the research staff becoming aware of the event.

Should the PI be unable to report within 24 hours, or is unavailable, any nominated person on the delegation log may send an unsigned SAE form. Further details should then be sent by site as soon as practically possible.

Events occurring before randomisation will not be recorded.

Any change of condition or other follow-up information should be added to the SAE eCRF in the database as soon as this information is available. Events will be followed up until the event has resolved or a final outcome has been reached. An outcome of 'unknown' is not considered to be an acceptable final outcome. An outcome of 'not yet resolved' is an acceptable final outcome for SAEs at database lock.

AEs or SAEs may be identified by the coordinating centre from the CRFs, either from specific questions or from answers within PROMs. If this occurs, the coordinating centre may query the site for details of the event for the purposes of the sites own clinical governance. This will be determined on a case-by-case basis, and the potential to do so will be included in the participant information sheet (PIS).

The Trial Manager (TM) will liaise with the investigator to compile all the necessary information. The trial coordinating centre is responsible for reporting any related and unexpected SAEs to the sponsor and REC within required timelines. Events which are

conclusively assessed by the PI's and CI's as possibly, probably, or definitely related to the trial intervention and are unexpected will be reported to the REC within 15 days.

4.1.5 SAEs Exempt from Reporting

As with AEs, SAEs will only be reported where there is an untoward medical occurrence in a participant related to their treated knee and to the treatment they receive in the trial (or any treatment for the knee) or related to trial processes. Other events that do not meet this definition will not be reported. Normal events defined in section 4.1.2 will not be reported as AEs or SAEs.

4.1.6 Assessment of Causality

A clinically qualified member of site staff that has been appropriately delegated by the PI should perform an assessment as to whether there is a possibility that the event has occurred as a result of the trial intervention. An independent assessment will also be performed by a delegate of the Sponsor. If either the PI's delegate or the Sponsors delegate determines that there is a possible causal relationship with the intervention or its associated procedures an expectedness assessment will be performed by a delegate of the Sponsor at WCTU.

The causality of SAEs (i.e., relationship to trial treatment) will be assessed by the investigator(s) on the SAE form using the descriptions in Table 3.

Table 3. SAE causality

Relationship to trial intervention	Description	
Unrelated	There is no evidence of any causal relationship	
Unlikely to be related	There is little evidence to suggest there is a causal relationship (e.g., the event did not occur within a reasonable time after administration of the trial intervention or device). There is another reasonable explanation for the event (e.g., the patient's clinical condition, other concomitant treatment).	
Possible relationship	There is some evidence to suggest a causal relationship (e.g., because the event occurred within a reasonable time after administration of the trial intervention or device). However, the influence of other factors may	

	have contributed to the event (e.g., the patient's clinical condition, other concomitant treatments).		
Probable relationship	There is evidence to suggest a causal relationship and the influence of other factors is unlikely.		
Definitely related	There is clear evidence to suggest a causal relationship and other possible contributing factors can be ruled out.		

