4. ADVERSE EVENT MANAGEMENT

4.1 Definitions

4.1.1 Adverse Events

An Adverse Event (AE) in this study will be defined as any untoward medical occurrence in a participant taking part in health care research, which does not necessarily have a causal relationship with the research. However, for the purposes of this trial, and to avoid unnecessary recording of events, we will only collect AEs or Serious Adverse events (SAEs) related to their treated knee and to the treatment they receive in the trial (or any treatment for their treated knee) or related to trial processes.

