4.3 Notification of deaths

All deaths where there may be a relationship between the trial interventions or the condition being studied (in this case, any knee condition, or an event related to the anaesthetic, surgery, hospital admission, physiotherapy) will be reported by the CI to the sponsor. This report will be as soon as the CI becomes aware of the event. Reporting processes to other organisations (REC and the manufacturer) will be as documented above."

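### For systemic serious events the site's relatedness judgement comes before the independent causality assessment, and the protocol states no provision for reporting deaths from any cause

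*Protocol*

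**What the plan says.** Collection is restricted on purpose. Protocol 4.1.1 gives the reason as "to avoid unnecessary recording of events" and sets the rule: "we will only collect AEs or Serious Adverse events (SAEs) related to their treated knee and to the treatment they receive in the trial", extended to any treatment of that knee and to trial processes. Under 4.1.3 an SAE "is an AE, as defined for this trial (see 4.1.1), that fulfils one or more of the following criteria", so the restriction carries over. The same section then restates it in different words: "we will only collect SAEs related to the participant's treated knee, to the treatment they receive in the trial", or to trial processes. Section 4.1.5 closes the list: "Other events that do not meet this definition will not be reported".

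For what is reported, 4.1.6 has a delegated site clinician assess causality and adds: "An independent assessment will also be performed by a delegate of the Sponsor". A possible relationship in the view of either one leads to an expectedness assessment. Table 3 grades relation to the trial intervention on five levels, the lowest being unrelated.

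On deaths, 4.3 requires notification of "All deaths where there may be a relationship between the trial interventions or the condition being studied", and it names anaesthetic, surgery, hospital admission and physiotherapy among the possible links.

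**The concern.** Two assessors with an either-is-enough rule protect against one error above all: a site wrongly deciding that an event had nothing to do with treatment. If that same decision also determines whether the event is reported, the protection does not operate for the events it governs.

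Systemic events are where this bites. With no evident knee link, their entry to the trial rests on perceived relation to treatment or trial processes. Site practitioners are unblinded (2.9), and 4.2 gives the principal investigator or delegate both the causality judgement and the duty to report what meets the trial criteria. Section 4.2 also asks the Data Monitoring Committee to find patterns that single cases would not reveal, yet single-case attribution decides which systemic events it receives. Adverse events are a secondary outcome (2.2.2). Anaesthetic and peri-operative harms arise mainly after surgery, so events lost at this step would probably make surgery look safer.

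**Working it through.** The protocol gives no figure on this point to reproduce, so the check follows an event through the text.

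1. **Entry.** An SAE must first be an adverse event under 4.1.1, which requires relatedness. Section 4.1.5 excludes the rest.
2. **Assessment.** Section 4.1.7 applies causality assessment only to SAEs that have been reported, and 4.1.6 places the investigator's grade on the SAE form. Without a form there is no second assessment.
3. **Two different questions.** The entry test covers the knee, any treatment of it, and trial processes. Table 3 asks only about the trial intervention. An event can therefore pass the first and be graded unrelated on the second.
4. **Outcome by type of event.**

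| Event and site's view | 4.1.3 wording (alternatives) | 4.1.1 and 4.1.5 wording (knee and treatment) |
|---|---|---|
| Knee event, linked to treatment | Both assessors | Both assessors |
| Knee event, not linked to treatment | Both assessors; the Sponsor's delegate can overrule the site | Not reported |
| Systemic event, linked to treatment | Both assessors | Excluded if read literally, although 4.1.2 and 4.1.7 plainly expect such events |
| Systemic event, not linked to treatment or trial processes | Not reported | Not reported |

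The fourth row is the gap, and it is the same under either wording. The second and third rows change with the wording, which is a separate inconsistency.

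5. **Deaths.** A death reaches the trial as an SAE only through step 1, or by notification under 4.3 when a link is thought possible. No section provides for a death outside both.
6. **Other routes.** Table 2 has adverse events completed by site and participant at 6, 12, 18 and 24 months, with medical note review to 24 months and a participant item on problems and complications. Section 4.1.4 lets the coordinating centre find events in forms and questionnaires and query the site case by case, for the site's own governance. Section 5.1 allows GP letters or routine data for non-responders, on complications and re-operations. Section 2.7.2 says routine NHS data may be searched. None of these requires an SAE form or a second causality opinion.

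**The case against.** The strongest reply is that this is a declared choice. Section 1.6 describes both packages as standard NHS care with ordinary risks, and 4.1.1 limits recording deliberately. The systemic events are named for sites in 4.1.7, and 4.1.2 covers harms of anaesthetic and post-operative care, so a site that dismissed a post-operative clot would be disregarding the protocol's own list. The death threshold is low, and a death after an anaesthetic would plausibly meet it. The routes in step 6 do not all depend on the site.

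Much of this stands. It rules out three stronger readings that a reader might infer:

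- *The independent assessor never sees the events that matter.* Under 4.1.3, knee-related SAEs that the site grades unrelated to the intervention are still reported and independently assessed.
- *Deaths enter only once judged related.* Section 4.3 asks only whether there may be a relationship.
- *Other deaths are not recorded anywhere.* The case report forms, data management plan, monitoring plan and health economic analysis plan are not shown and may capture them. For the same reason, an effect on QALYs cannot be claimed.

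What the reply does not meet is the fourth row of the table. Naming event types tells sites what may be related. It does not have the Sponsor's delegate review the cases where a site concludes otherwise.

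**Conclusion.** The point holds in limited form. For non-knee systemic serious events, 4.1.6 cannot correct a site's decision that the event is unrelated, and the protocol states no provision for deaths from any cause. It is a weakness in a deliberate design, and worth amending.

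No size can be given. A reader might apply the 3-7% complication rate for ligament reconstruction (1.2.2) to half the sample, 276 / 2 = 138. That gives 0.03 x 138 = 4.1 to 0.07 x 138 = 9.7 events, and one could then say that two missed events are 20% to 50% of the surgical total. The documents do not support this. The two events are assumed. The rate includes infection and reoperation, much of which the filter already admits as knee events. The base also assumes that all 138 have that operation, and 2.8.1.2 gives a different rate, about 3-5%.

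The direction, towards flattering surgery, is a reasoned expectation and has not been shown. The extent of the gap also depends on how readily sites call an event related, since the protocol sets no threshold for the entry test. A site that reports on any possibility would lose few events.

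**What to change.** Amend 4.1.3, 4.1.5 and 4.3 so that sites report, in both arms, from randomisation to 24 months and without first judging relatedness:

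- (a) every death, whatever the cause;
- (b) every serious event of the systemic types already listed in 4.1.7: anaesthetic events, chest infection, stroke or cardiac event, and thrombosis.

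Section 4.1.3 should say that these count as SAEs despite the restriction in 4.1.1; otherwise its cross-reference would exclude them again. Both assessors then assign causality under 4.1.6. Keep the relatedness filter for all other events. The period matches the SAE window already in 4.1.4.

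The rule should not be confined to the time after a knee operation. That would make ascertainment depend on treatment: a late chest infection would count in an operated participant and not in one who had no surgery.

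Separately, reconcile the knee-and-treatment wording of 4.1.1 and 4.1.5 with the alternatives listed in 4.1.3, so that sites apply one test.

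The cost is a protocol amendment and some extra SAE forms, including some for events that prove unrelated. In 276 mostly young participants the number should be small, which is an assumption.
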